3.2.3 Randomization

After the pre-intervention assessments, participants will be randomized into two groups: app group (GA) and control group (CG). This randomization will be performed in blocks, according to sex and pre-intervention blood pressure, from a table of random numbers, by researchers who are not directly involved with the recruitment of participants and with data collection.

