3.2 Effectiveness testing

3.2.1 Participants

This stage of the study will involve the performance of a randomized and controlled clinical trial that will be conducted at the Sports Center of the Federal University of Santa Catarina, Florianópolis, SC. Based on a previous behavior change study¹⁹, taking systolic blood pressure as a reference, taking into account an effect size of 0.8, power of 80% and alpha error of 0.05, the estimated sample size is 52 participants (26 per group). The recruitment of these participants will be based on the dissemination of the research in the local media (radio, newspapers, internet) and in social groups, distribution of pamphlets and posting of posters in the vicinity of the evaluation sites.

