3.2.12 Statistical analysis plan (SAP)

Initially, the normality and homogeneity of variance will be analyzed using the Shapiro-Wilk and Levene tests, respectively. For data that do not have a normal distribution, logarithmic transformation will be performed. Student 's t test for independent samples and the chi-square test will be used to compare the groups at the pre-intervention moment, regarding continuous and categorical variables, respectively.

For the Intra and inter-group comparisons of quantitative and qualitative variables, the method of generalized estimation equations will be used (group: GA and GC; time: pre and post-intervention assessments; interaction (group vs. time), after confirming the appropriate assumptions. In all analyses, when a significant effect is verified, the Newman-Keuls post-hoc test will be used, with a P value <0.05 being considered significant.

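### Randomization is blocked on sex and baseline blood pressure, but the planned GEE adjusts for neither and gives up precision on systolic pressure that would cost no extra participants

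*Combined protocol and SAP*

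**What the plan says.** Section 3.2.3 (Randomization): "This randomization will be performed in blocks, according to sex and pre-intervention blood pressure". It does not give the cut-points, the block size, or whether the blood pressure (BP) factor is systolic or diastolic.

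Section 3.2.12 (SAP): for comparisons within and between groups, "the method of generalized estimation equations will be used", with these terms: "group: GA and GC; time: pre and post-intervention assessments; interaction (group vs. time". It names no covariate, stratification factor, working correlation or type of standard error. Baseline values otherwise appear only in t and chi-square tests comparing the groups before the intervention.

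Section 3.2.1 (Participants) sizes the trial "taking systolic blood pressure as a reference, taking into account an effect size of 0.8, power of 80% and alpha error of 0.05", and "the estimated sample size is 52 participants (26 per group"). It does not say whether 0.8 is in SDs of the post-intervention value or of the change. It gives no pre/post correlation and no allowance for dropout.

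**The concern.** In the planned model, baseline SBP is the first of two repeated responses and the groups are free to differ on it. It is not a covariate. The interaction therefore subtracts the whole baseline value, a weight of 1, whatever the data show about how strongly baseline predicts the post-intervention value. Baseline adjustment estimates that weight and is more precise for any r below 1.

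The model also omits the BP factor on which allocation is blocked. Blocking makes the groups more alike at baseline and so reduces the true variability of the contrast, but a model-based standard error does not reflect this and comes out too large.

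The trial has just over 80% power at 52 participants and no stated reserve. Section 3.2.2 also treats a change of antihypertensive drug or dose during the study as a ground for exclusion, so the analysed number may be lower. At stake are a wider confidence interval and a higher chance of missing a real SBP effect than the same data require.

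**Working it through.** **Inputs.** From section 3.2.1: standardised effect 0.8, 80% power, alpha 0.05, 26 per group. From section 3.2.12: model terms group, time, group × time. Assumed, because the documents do not give them: r = 0.3, 0.5, 0.7, 0.8; equal pre and post SDs; complete data; no log transformation; a two-sided test.

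**The plan's own figure.** A two-sided two-sample t test (noncentral t) with d = 0.8 has 79.1% power at 25 per group and 80.7% at 26. The stated 52 reproduces. A one-sided test would need about 20 per group (normal approximation) and does not reproduce it.

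**What the interaction estimates.** Two groups at two times give four cell means and four mean parameters, so the model is saturated. In a test dataset the GEE interaction coefficient was 0.32489 under both independence and exchangeable working correlation, identical to the directly calculated difference in mean change. A sex main effect cancels out of this term, so the loss comes from baseline BP.

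**Closed form, ignoring blocking.** In post-value SD units the variance of the group effect is proportional to:

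- raw change: 2(1 − r)
- baseline-adjusted: 1 − r²
- ratio, adjusted to change: (1 + r)/2

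The standardised effects are 0.8/√(2(1 − r)) for change (df 50) and 0.8/√(1 − r²) for adjusted (df 49) if 0.8 is in post-value SDs. If 0.8 is in change SDs they are 0.8 and 0.8·√(2/(1 + r)). At r = 0.5 in post-value SDs: 0.8/√1 = 0.80 gives 80.7%, and 0.8/√0.75 = 0.924 gives 90.4%.

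| r | Variance ratio | Power, 0.8 in post-value SDs: change vs adjusted | Power, 0.8 in change SDs: change vs adjusted |
|---|---|---|---|
| 0.3 | 0.65 | 66.7 vs 84.2% | 80.7 vs 93.9% |
| 0.5 | 0.75 | 80.7 vs 90.4% | 80.7 vs 90.4% |
| 0.7 | 0.85 | 95.5 vs 97.7% | 80.7 vs 86.6% |
| 0.8 | 0.90 | 99.4 vs 99.7% | 80.7 vs 84.6% |

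At r = 0.5, adjustment is worth 26/0.75 ≈ 35 per group.

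**With blocking.** Simulation, n = 52: sex 50:50, bivariate normal SBP with unit SDs, strata of sex by SBP above or below the median, permuted blocks of 4 (strata and block size assumed). There were 20,000 null and 10,000 alternative trials per setting. The change contrast was tested by pooled t; the adjusted contrast by least squares on group, baseline SBP and sex.

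| r | Power, post-value SDs | Power, change SDs | True variance reduction | Mean 95% CI half-width (SD) |
|---|---|---|---|---|
| 0.3 | 69.2 vs 83.9% | 83.2 vs 93.8% | 18% | 0.66 to 0.53 |
| 0.5 | 82.4 vs 89.7% | 82.3 vs 89.8% | 12% | 0.56 to 0.48 |
| 0.7 | 96.2 vs 98.0% | 81.6 vs 86.1% | 6% | 0.43 to 0.40 |
| 0.8 | 99.6 vs 99.8% | 81.2 vs 84.0% | 4% | 0.35 to 0.33 |

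Calibration of the unadjusted contrast at r = 0.3, 0.5, 0.7, 0.8:

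- Model-based SE: too large by 12, 9, 5, 2%; type I error 2.8, 3.1, 3.8, 4.5%.
- Uncorrected robust z: SE too large by 10, 6, 3, 0%; type I error 3.5, 4.1, 4.7, 5.4%.

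The adjusted test held 4.6 to 5.1%. A separate simulation of 6,000 trials per setting, adjusting for baseline only, agreed: at r = 0.5 the change contrast had a mean SE of 0.276 against a true SD of 0.256, and power was 82.8 vs 90.1%.

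**The case against.** The planned GEE is a valid and common analysis, N reproduces, and nothing here shows bias. In the simulation the planned contrast falls below 80% power in only one of eight settings (r = 0.3, post-value SDs). All of this stands: the loss is relative to a better use of the same data, not a failure to reach the design target.

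GEE is usually reported with robust standard errors, and the tables use a pooled t. Rerunning the design with uncorrected robust z (8,000 trials per setting) gave, for r = 0.3, 0.5, 0.7, 0.8:

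- post-value SDs: 71.5 vs 83.4, 84.4 vs 89.8, 96.9 vs 97.7, 99.6 vs 99.7%
- change SDs: 85.8 vs 94.1, 84.6 vs 90.1, 84.4 vs 86.5, 83.5 vs 84.1%

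The gain shrinks to about 5.5 points at r = 0.5 and 0.1 to 2.1 points at 0.7 or above. That also stands, though part of it reflects the slightly liberal uncorrected z test at high r, and the SAP does not say which SE applies.

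The BP procedure in section 3.2.7 (repeated readings on two days) and the eight-week follow-up may favour a higher r, which makes 0.3 the least favourable assumption. This is fair, but r remains unknown.

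Only the stratifying BP outcome was simulated, so the figures do not carry over to other outcomes. The unnamed BP stratifier does not invalidate an adjusted diastolic model. Within-group comparisons, which the SAP also plans, need the constrained-baseline form because a model of the post-intervention value alone does not supply them.

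**Conclusion.** The concern holds. As written, the SBP contrast is a difference in raw change that leaves out baseline adjustment and the BP blocking factor. The consequence is lost precision in the conservative direction: no bias, no material type I inflation and no error in N.

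The loss is material at low to moderate r. At r = 0.5 it is about 7 points of t-based power, or about 5.5 with robust z. At r of 0.7 or more it is under 2 points if 0.8 is in post-value SDs; in change SDs it is about 3 to 4.5 points t-based, and less with robust z.

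These sizes rest on the assumed r, the assumed strata and block size, complete data and untransformed SBP. With missing post-intervention values the working correlation would also matter, and none is named. The change should be made, but the trial does not depend on it. Confidence in the size is medium because r is unknown.

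**What to change.** Amend section 3.2.12 before data are analysed:

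- **SBP and diastolic BP:** make the primary contrast the group effect on the post-intervention value, adjusted for the continuous baseline value of the same outcome and for sex.
- **Other continuous outcomes:** adjust for their own baseline plus the stratification factors (sex and baseline BP).
- **Alternative:** a repeated-measures model constrained to equal baseline means, with the same factors. This also keeps the within-group comparisons.
- **Inference:** use t-based or small-sample-corrected inference, name the SE, and report the group coefficient with its 95% CI.
- **Section 3.2.3:** state which BP measure and cut-point define the blocks, so that the covariates match the design.

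The cost is SAP wording and a few degrees of freedom. N stays at 52 and every variable is already collected.

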3.2.4 Experimental Design

Participants will be submitted, before the start of the intervention (pre-intervention), to laboratory blood pressure assessments, adherence to drug treatment, physical activity and lifestyle. Afterwards, the GC will participate in an informative lecture on healthy habits and general aspects of SAH control and treatment, while the GA will be submitted to the use of the application for eight weeks. At the end of these eight weeks of intervention (post-intervention), the participants of both groups will be reassessed in all the items analyzed at the pre-intervention moment. It is noteworthy that the researchers involved with the evaluations and data analysis will be blinded regarding the randomization of the participants.

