3.1 General Description

The main focus of the application is to assist in the treatment of patients with SAH. The application will address the components of adherence to medication use, blood pressure monitoring and promotion/monitoring of physical activity. In addition, health education tips will be provided, including guidelines for reducing sodium consumption, adopting an adequate and healthy diet, controlling body weight, moderate alcohol consumption and stress management, in accordance with the recommendations of the main guidelines related to the theme ^{1, 3}.

After downloading, patients must manually enter demographic data (date of birth, sex), their body mass and height, information regarding the use of the drugs used, the presence of comorbidities (diabetes, dyslipidemia, chronic kidney disease, coronary artery disease, peripheral arterial disease, among others). In addition, the user must enter data related to their lifestyle, including information about: physical activity, nutrition, alcohol consumption, tobacco use, stress and relationships, according to an adapted version of the Fantastic lifestyle.

Based on this information entered by the patient (*input*), the application will issue reminders: a) for the use of the medication(s), according to the time registered by the patient, daily; b) to perform blood pressure measurements. The patient will be instructed to take blood pressure measurements while sitting, in a calm environment, after five minutes of rest, with the bladder emptied and there is at least 30 minutes of abstention from food, cigarettes and/or alcoholic and caffeinated beverages. Such measured BP values must be entered in the application and, if a BP level above the recommended values is identified, the insertion of the importance of the correct use of antihypertensive medication and adoption of a healthy lifestyle will increase. It will also be suggested that you consult your doctor for possible medication adjustments.

In addition, the user will be given the possibility to self-monitor their physical activities and, based on this information, the application will generate

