feedback informing whether or not the user has reached the recommendations currently in force^{17,18}. If the user does not meet the recommendations throughout the week, illustrative messages or videos will be generated with stimuli and guidelines for the patient to increase their level of physical activity, according to such recommendations. Illustrative messages or educational videos will also be made available with tips on healthy living habits, including recommendations for body weight control, reducing sodium consumption, adopting healthy eating habits, stress control and smoking cessation, as recommended by the main guidelines related to thematic^{1,3}.

Reports for the patient regarding blood pressure values and physical activity will be available, showing the evolution over time. For programmers and researchers, these same reports will also be generated, in addition to reports with application usage statistics and general user characteristics (*business intelligence*), so that, with this information, the system can be feedback.

Patients will be able to designate family members and/or friends to have access to the data captured and generated by the application, so that these people can provide social support for the treatment of hypertensive patients. In addition, a communication channel will be opened between patients that the application identifies in closer locations, in case the patient wants to share doubts, challenges and achievements.

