3.2.2 Screening

As inclusion criteria, participants must be over 18 years old, have a clinical diagnosis of SAH³, have been using antihypertensive medication for more than three months, and cannot be involved in the regular practice of physical activities. In addition, participants must have a *smartphone*, they must not have cognitive disabilities that limit the understanding and use of an application and/or physical limitations that make it difficult to practice physical activities. Changes in the type and/or dose of antihypertensive drugs used during the study will be considered as exclusion criteria.

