3.2.6 Control group

The GC, in turn, will participate in a single lecture, in the first week of the intervention, with basic guidelines related to the key points of the treatment of SAH, including the importance of medication adherence, monitoring of blood pressure values and/or capillary glucose, lifestyle modifications linked to physical activity, eating habits, smoking cessation, stress management and moderate alcohol consumption.

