3.2.11 Evaluation and patient satisfaction with the application

At the end of the intervention, patients undergoing the GA will be invited to answer an adapted version of the assessment scale for *smartphone applications* for health care, proposed by Jim and Kim ²⁴, which contains 23 items in total, related to the assessment of content, objectivity, interface design, writing style and technology, with response options ranging from zero (not at all) to four (a lot), generating an overall score. From there, all adjustments that are considered relevant will be made so that the final version of the application will be available on Apple iTunnes and Google Play.

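### Neither arm is asked about symptoms, falls, injuries, unplanned care or hospital admission, so the trial cannot report clinical events by group before the app is released

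*Combined protocol and SAP*

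**What the plan says.** Section 3.2.4 submits participants before the intervention "to laboratory blood pressure assessments, adherence to drug treatment, physical activity and lifestyle". After that, "the GA will be submitted to the use of the application for eight weeks", and at the end of that period "the participants of both groups will be reassessed in all the items analyzed at the pre-intervention moment". Sections 3.2.7 to 3.2.10 give the instruments: an automatic blood pressure device, an eight-item adherence scale, accelerometry and a lifestyle questionnaire.

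Section 3.2.11 adds a 23-item rating scale for the app group only. It covers the app's content and objectivity, its interface, its writing and its technology. The section continues: "From there, all adjustments that are considered relevant will be made so that the final version of the application" can go to the public stores. Section 3 describes the same sequence of test, adjustment and release.

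Contact during the eight weeks differs by arm. The control group "will participate in a single lecture, in the first week of the intervention". In the app group, section 3.1 describes daily medication reminders and home blood pressure readings ("Such measured BP values must be entered in the application"). It also describes a suggestion to see a doctor when readings are high and, for users below the activity recommendations, "guidelines for the patient to increase their level of physical activity". Under section 3.2.2, participants "cannot be involved in the regular practice of physical activities".

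The analysis plan in section 3.2.12 contains no safety analysis. The ethics section, 3.4, covers committee submission, the national resolution and registration; it does not describe how harms are collected or reported.

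**The concern.** The app encourages two things in treated hypertensive adults who do not exercise regularly: fuller use of antihypertensive drugs and more physical activity. Either could plausibly produce symptoms or events such as dizziness, a fall, an injury during exercise or an unplanned visit. Nothing at baseline or follow-up asks about these, and an analyst cannot later reconstruct them from two blood pressure assessments, an adherence score, accelerometer minutes and a lifestyle score.

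The timing adds to the problem. This trial is the randomised comparison that precedes public release, and the adjustments before release follow an app rating scale with no harm content. As planned, the report could describe benefit on the chosen outcomes but could not say how many people in each group had a clinical event. If reports do arrive unasked, the two arms differ in how much contact they have with the study material, so capture might be unequal.

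**Working it through.** **1. The plan's own figure.** Section 3.2.1 gives an effect size of 0.8, 80% power, alpha 0.05 and 52 participants (26 per group). Sidedness is not stated; two-sided is assumed.
- Normal approximation: n per arm = 2(1.960 + 0.842)² / 0.8² = 24.5, rounded up to 25.
- Exact t test: power is 0.791 at 25 per arm and 0.807 at 26, so 26 per arm and 52 in total.

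The figure reproduces. The plan gives no harm rate and no dropout allowance. Asking about harms does not change the sample size.

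**2. Where a harm question could sit.**
- 3.2.7: blood pressure readings on two days. No event question.
- 3.2.8: adherence scale. No event question described.
- 3.2.9: seven days of accelerometry. No event question.
- 3.2.10: lifestyle questionnaire on nutrition, activity, prevention, relationships and stress. No event question described.
- 3.2.11: app rating scale, app group only. No harm domain.
- 3.2.12 and 3.4: no safety analysis and no harm reporting.

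**3. What 26 app users could show if all were asked and recalled every event.**
- Zero events of a given type: one-sided 95% upper bound = 1 − 0.05^(1/26) = 0.109, or 10.9%.
- Chance of at least one event at true risk p = 1 − (1 − p)^26. The risks below are assumed; none is in the documents.
  - p = 1%: 23%
  - p = 2%: 41%
  - p = 5%: 1 − 0.95^26 = 0.736, or 74%
  - p = 10%: 1 − 0.90^26 = 0.935, or 94%

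**4. The same with incomplete follow-up.** Assume 15% loss: 26 × 0.85 = 22.1, taken as 22.
- Upper bound: 1 − 0.05^(1/22) = 0.127, or 12.7%.
- p = 5%: 1 − 0.95^22 = 0.676, or 68%.

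The figures in step 3 are therefore upper limits on what the question would deliver, and under-recall would lower them further.

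**5. Unequal capture of unsolicited reports.** If the true risk is equal in both arms and the chance that an event becomes known is a (app) and c (control), the app group's share of known events is a / (a + c).
- Equal capture: 50%.
- Assumed 50% versus 25%: 67%.
- Assumed 50% versus 10%: 83%.

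The documents give neither a nor c. This shows only that unequal capture could mislead; it does not estimate by how much.

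**The case against.** The best case for the plan is that this is an eight-week behavioural app, the trial assigns no drug, and the comparison of planned outcomes is valid without harm data. Participants have taken antihypertensives for more than three months, and those with physical limitations that make activity difficult are not eligible (3.2.2). The control lecture also promotes adherence and activity (3.2.6), so the arms differ in intensity of prompting. All of this stands. It limits the weight of the point but leaves the gap in place.

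A reader might infer four stronger things that the documents do not support.
- *That harms which surface will come mainly from the app arm.* No section describes a route for reporting symptoms to the team through the app. The rating scale has no symptom domain, the communication channel in 3.1 is between patients, and the reassessment visit is the same for both arms with blinded evaluators. Unequal capture is possible, but its size cannot be computed.
- *That the trial can say nothing about harm.* Systolic and diastolic pressure are re-measured in both arms, so a mean worsening or a large mean fall would be visible. Symptoms and clinical events are what is missing.
- *That after release only downloads and star ratings are followed.* Section 3.3 limits the formal evaluation to these, but 3.1 also gives researchers reports on blood pressure, activity and usage. Those are not harm reports, yet they exist.
- *That the trial sample is known to include coronary, arterial or kidney disease.* The comorbidity list in 3.1 is a data-entry field for app users and does not describe the participants.

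**Conclusion.** The point holds in this form: sections 2.1 to 3.4 plan no question about symptoms, falls, injuries, unplanned care or admission in either arm, so clinical events by group would not be available before adjustment and release. The opening pages and consent forms were not in the text examined, so this concerns the design, assessment, analysis and ethics sections. It is a gap in safety information that is cheap to close. It does not invalidate the outcome comparison.

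The gain from closing it is modest. With all 26 app users assessed and full recall, zero events would exclude risks above 10.9%, and an event of assumed 5% risk would be seen with at most 74% probability. With 22 assessed, these become 12.7% and 68%. An event of 1% risk would usually be missed (23% even with complete capture).

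One related inconsistency bears on who would be asked. Section 3.2.2 treats a change in antihypertensive type or dose as grounds for exclusion, while 3.1 has the app suggest seeing a doctor about possible adjustments. Participants whose treatment changed could leave the data, possibly more often in the app group. These sections must be reconciled.

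**What to change.** Add to 3.2.4 a short fixed-wording questionnaire at the existing post-intervention visit, covering the past eight weeks: symptoms such as dizziness or fainting; falls; injury or chest symptoms during activity; unplanned medical or emergency visits; hospital admissions.

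- Ask it identically of every randomised participant in both arms, including anyone excluded under 3.2.2 for a drug change.
- Have the blinded evaluator ask it after the blood pressure measurements are complete, so that an answer that reveals the group cannot affect those readings.
- Add to 3.2.12 one descriptive table of counts by randomised group, with the number asked in each group and no formal test.
- State that the table is available before the 3.2.11 adjustments and release.

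This costs about five questions and one table, with no extra visit, staff or participants. The downside is a few minutes per participant and imperfect recall over eight weeks, which should be noted when the counts are reported.
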